7.1 Halting Criteria and Discontinuation of Study Intervention

7.1.1 Study Halting Criteria

Additional enrollment and study interventions/administration of study products in this trial will be halted for SMC review/recommendation if any of the following are reported:

- Any subject experiences ulceration, abscess, or necrosis at the injection site related to study product administration.
- Any subject presents with laryngospasm, bronchospasm, hypotension or anaphylaxis occurring within 24 hours following product administration that is considered related to study product.
- Two or more subjects experience generalized urticaria (defined as occurring at more than two body parts) within 72 hours after administration of study product that is considered related to study product.
- Any subject experiences an SAE after administration of study product and prior to the subject's last visit that is considered related to study product.
- Two or more subjects who received at least one dose of study vaccine to date, cumulative to all study vaccine administrations, across all treatment arms, experience the same Grade 3 (unsolicited AE or safety laboratory), in the same HLT by MedDRA coding, considered related to study product.

This trial will also be halted for SMC review/recommendation if, within 7 days after administration of either study vaccination, any of the following occurs:

- Three or more subjects who received at least one dose of study vaccine to date, cumulative to all study vaccine administrations, across all treatment arms, experience the same severe (Grade 3) study vaccine-related injection site reaction. Erythema and induration (hardness)/edema (swelling) will also be measured in mm but size will not be used as halting criteria.
- Three or more subjects who received at least one dose of study vaccine to date, cumulative to all study vaccine administrations, across all treatment arms, experience the same severe (Grade 3) study vaccine-related subjective systemic reaction, for which the severity (grade) is corroborated by study personnel.
- Three or more subjects who received at least one dose of study vaccine to date, cumulative to all study vaccine administrations, across all treatment arms, experience the same severe (Grade 3) study vaccine-related quantitative systemic reaction.

Grading scales for solicited injection site and systemic (subjective and quantitative) reactions are included in Section [8.5.1.1](#).

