7.1.2 Individual Halting Criteria

Individual Halting Criteria must be reviewed by the site PI prior to administration of the second study vaccination for each subject. It is the responsibility of the site to ensure that any subject meeting the below criteria are discontinued from receiving study product; however, the Emmes BMM or safety monitor may be consulted as needed.

The second study vaccination will not be administered to a subject if any of the following criteria are met, as determined by the site PI:

- Serious adverse event associated with study vaccination.
- Pregnancy in a female subject.
- Type 1 hypersensitivity associated with study product.
- Grade 3 systemic reaction associated with study product.
- Grade 3 local reaction (with the exception of erythema/induration) associated with study product (e.g., pain).
- Grade 2 or higher fever within the first 24 hours following the initial vaccination.
- Medical condition for which continued participation, in the opinion of the site principal investigator or appropriate sub-investigator, would pose a risk to the subject or would be likely to confound interpretation of the results.
- Presence of signs or symptoms that could confound or confuse assessment of study vaccine reactogenicity. For subjects with injection site or systemic signs or symptoms, or with an acute illness, including but not limited to an oral temperature greater than or equal to 100.4°F, the second study vaccination should be postponed/deferred until signs, symptoms, or acute illness have resolved and still within the acceptable protocol-specified window for that visit. If outside this window, the Blinded Medical Monitor must first approve the second study vaccination and the documentation of approval should be filed in the subject's chart.
- Any unresolved or continuing solicited or unsolicited Grade 3 adverse event after first vaccination. An unresolved or continuing Grade 1 or Grade 2 adverse event is permissible unless, in the opinion of the site principal investigator or appropriate subinvestigator, it would render study vaccination unsafe or interfere with the evaluation of responses.
- Grade 2 or higher clinical safety laboratory result that does not decrease to Grade 1 or below prior to the second study vaccination. For a subject to receive the second study vaccination, the most recently evaluated clinical safety laboratory values obtained prior to the second study vaccination must be Grade 1 or less. The

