8.2.2 Safety Clinical Laboratory Tests

Safety labs will be conducted on blood samples obtained on Days 4 and 15 after each vaccination and on the day of, but prior to, administration of the first and second vaccination (day 29 after first vaccination). Safety labs include hematology tests (hemoglobin, WBC, and platelet count) and blood chemistry tests (sodium, potassium, bicarbonate, calcium, creatinine, glucose [non-fasting], ALT, AST, and total bilirubin).

Urine will be tested by dipstick to evaluate glucose, protein, blood, and leukocyte esterase on days 1, 15 and 29 after first vaccination and day 15 after second vaccination.

Safety labs will be tested locally by Duke University Health System Clinical Laboratories.

For laboratory values outside the site's reference ranges, the site PI will document clinical significance in the eCRF. Any result that is deemed clinically significant but does not meet the protocol's grading criteria ([Appendix A](#)) should either be repeated by the study site, or the subject referred for appropriate clinical follow-up.

For any result that meets the protocol's grading criteria (whether or not it is deemed clinically significant), the PI will also assess relationship to study product, action taken with product, and whether the subject was discontinued due to the event. Graded laboratory abnormalities should be followed until either a return to normal or are judged to be stable, as determined by the PI.

In the absence of a diagnosis, any clinical safety laboratory test result that meets the definition of an SAE as determined by the investigator (e.g., life-threatening) must be reported as an SAE using the AE/SAE form set.

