8.5.3.1 Seriousness and Severity of Event

Event seriousness will be determined according to the protocol definition of an SAE (Section [8.5.1](#)). All AEs or SAEs will be assessed for severity, according to the toxicity grading scales in [Appendix A](#).

For adverse events (AEs) not included in the protocol defined grading system, the following guidelines will be used to describe severity.

- Mild (Grade 1): Events that are usually transient and may require only minimal or no treatment or therapeutic intervention and generally do not interfere with the subject's usual activities of daily living.
- Moderate (Grade 2): Events that are usually alleviated with additional specific therapeutic intervention. The event interferes with usual activities of daily living, causing discomfort but poses no significant or permanent risk of harm to the research participant.
- Severe (Grade 3): Events interrupt usual activities of daily living, or significantly affects clinical status, or may require intensive therapeutic intervention. Severe events are usually incapacitating.

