9.4.2 Analysis of Primary Outcome Measures (Safety)

Solicited AEs and laboratory toxicities will be analyzed by taking the most severe response over the follow-up period, dichotomizing into a binary variable (none or mild versus moderate or severe) and using exact confidence intervals to summarize the reactogenicity and toxicity rates. Tabular and graphical summaries of events will be presented for each solicited symptom, by type (local/systemic/toxicity), severity (none or mild, moderate or severe), and time point post-vaccination.

Unsolicited AEs will be coded by the Medical Dictionary for Regulatory Activities (MedDRA) for preferred term and system organ class. The rate and exact 95% confidence intervals of AEs in aggregate, and by MedDRA categories, will be computed. SAEs will be reported by a detailed listing showing the type, MedDRA coding, relevant dates (vaccination and adverse event), severity, relatedness, and outcome for each event. Primary outcome measures include:

- Occurrence of all serious adverse events (SAEs) at any time during the study.
- Occurrence of all Grade 3 unsolicited adverse events (AEs) from first vaccination through day 29 after the second vaccination.
- Occurrence of all Grade 3 laboratory toxicities from first vaccination through day 15 after the second vaccination.
- Occurrence of solicited local AE and reactogenicity signs and symptoms in the 7 days after each vaccination.
- Occurrence of solicited systemic AE and reactogenicity signs and symptoms in the 7 days after each vaccination.
- Occurrence of any AE through day 29 after the second vaccination.

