APPENDIX A

Toxicity Tables

ABBREVIATIONS: Abbreviations utilized in the Table:

ULN = Upper Limit of Normal

LLN = Lower Limit of Normal

NOTE: For any of the lab values listed below if the Grade 1 value conflicts with the ULN or LLN value, the ULN or LLN value takes precedence and the event will not be considered a Grade 1 Adverse Event.

1. Laboratory Values

Hematology

Table 11. Hematology toxicity table

Parameter	Unit of measure	Abnormality	Mild (Grade 1)	Moderate (Grade 2)	Severe (Grade 3)
WBC	cell/mm ³	High	> 9,800 and ≤ 15,000	> 15,000 and ≤ 20,000	> 20,000
		Low	≥ 2,500 and < 3,200	≥ 1,500 and < 2,500	< 1,500
HgB (female)	g/dL	Low	≥ 11.0 and < 12.0	≥ 9.5 and < 11.0	< 9.5
HgB (male)	g/dL	Low	≥ 12.0 and < 13.7	≥ 10.0 and < 12.0	< 10.0
Platelets	cell/mm ³	Low	≥ 120,000 and < 150,000	≥ 100,000 and < 120,000	< 100,000

Blood Chemistries

Table 12. Blood chemistries toxicity table

Parameter	Unit of Measure	Abnormality	Grade 1	Grade 2	Grade 3
Sodium	mmol/L	High	146 to < 150	150 to < 154	≥ 154
		Low	130 to < 135	125 to < 130	< 125
Potassium	mmol/L	High	5.1 to < 6.0	6.0 to < 6.5	≥ 6.5
		Low	3.0 to < 3.5	2.5 to < 3.0	< 2.5
Bicarbonate	mmol/L	Low	16 to < 21	11 to < 16	< 11
Calcium	mg/dL	High	10.3 to < 11.5	11.5 to < 12.5	≥ 12.5
		Low	7.8 to < 8.7	7.0 to < 7.8	< 7.0
Random glucose	mg/dL	High	> 140 and ≤ 160	> 160 and ≤ 200	> 200
		Low	≥ 60 and < 70	≥ 55 and < 60	< 55
Bilirubin	n/a	High	> 1.5 and ≤ 2.0 x ULN	> 2.0 and ≤ 2.5 x ULN	> 2.5 x ULN
Creatinine ¹ (female)	mg/dL	High	> 1.0 and < 1.8	≥ 1.8 and < 2.0	≥ 2.0

Parameter	Unit of Measure	Abnormality	Grade 1	Grade 2	Grade 3
Creatinine ¹ (male)	mg/dL	High	> 1.3 and < 1.8	≥ 1.8 and < 2.0	≥ 2.0

¹Creatinine below the LLN is not considered an abnormality.

Liver Enzymes

Table 13. Liver enzymes toxicity table

Parameter	Unit of Measure	Abnormality	Grade 1	Grade 2	Grade 3
AST	n/a	High	1.1 - <2.0 x ULN	2.0 – <3.0 x ULN	3.0 – 8.0 x ULN
ALT	n/a	High	1.1 - <2.0 x ULN	2.0 – <3.0 x ULN	3.0 – 8.0 x ULN

Urine dipstick

Table 14. Urine dipstick toxicity table

Parameter	Unit of Measure	Abnormality	Grade 1	Grade 2	Grade 3
Protein ¹	n/a	High	1+	2+	> 2+
Glucose	n/a	High	1+	2+	> 2+
Blood ²	n/a	High	1+	2+	>2+
Leukocyte esterase ²	n/a	High	1+	2+	>2+

¹Trace protein not considered exclusionary at screening.

²Not included as screening labs, only as safety labs.

2. Clinical Adverse Events

Cardiovascular

Table 15. Cardiovascular toxicity table

Parameter	Unit of Measure	Abnormality	Grade 1	Grade 2	Grade 3

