3.2. Endpoints

Primary Outcome Measures:

- Occurrence of all serious adverse events (SAEs) at any time during the study
- Occurrence of all Grade 3 unsolicited adverse events (AEs) from first vaccination through Day 29 after the second vaccination
- Occurrence of all Grade 3 laboratory toxicities from first vaccination through Day 15 after the second vaccination
- Occurrence of solicited local AE and reactogenicity signs and symptoms in the 7 days after each vaccination
- Occurrence of solicited systemic AE and reactogenicity signs and symptoms in the 7 days after each vaccination
- Occurrence of any AE through Day 29 after the second vaccination

Secondary Outcome Measures:

- Percentage of subjects achieving seroconversion ($\geq 1:10$ in plaque reduction neutralizing titer [PRNT₅₀] titer, at Day 29 after first vaccination and at Day 29 after second vaccination
- Geometric mean neutralizing titers at days 15 and 29 after first vaccination and at Days 15, 29, and 57 following second vaccination
- Reverse cumulative distribution curve of neutralizing titers on Days 15 and 29 after first vaccination and at Days 15, 29 and 57 after the second vaccination for each dose group and for all dose groups combined

Exploratory Outcome Measures:

- Geometric mean neutralizing titers at Day 180 following second vaccination
- Reverse cumulative distribution curve of neutralizing titers on Day 180 after the second vaccination for each dose group and for all dose groups combined

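### Grade 3 for AST and ALT stops at 8.0 x ULN with no Grade 4 above it, so the worst liver-enzyme results have no laboratory grade

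*Protocol*

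**What the plan says.** Protocol Appendix A ("Table 13. Liver enzymes toxicity table") gives the same bands for AST and ALT: Grade 1 from 1.1 to below 2.0 x ULN, Grade 2 from 2.0 to below 3.0 x ULN, and Grade 3 from 3.0 to 8.0 x ULN. There is no Grade 4 column, and no note places higher values. SAP section 8 refers back to the protocol for grading scales and adds none.

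Several rules depend on the grade:

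- **Primary endpoint** (Protocol section 3, SAP 3.2): "Occurrence of all Grade 3 laboratory toxicities from first vaccination through Day 15 after the second vaccination".
- **Primary safety analysis** (Protocol 9.4.2): "laboratory toxicities will be analyzed by taking the most severe response over the follow-up period, dichotomizing into a binary variable", the two classes being none or mild and moderate or severe.
- **Investigator assessment** (Protocol 8.2.2): for a result that meets the grading criteria, "whether or not it is deemed clinically significant), the PI will also assess relationship to study product".
- **Follow-up** (Protocol 8.2.2): "Graded laboratory abnormalities should be followed until either a return to normal or are judged to be stable".
- **Study halting** (Protocol 7.1.1): two or more vaccinated subjects who "experience the same Grade 3 (unsolicited AE or safety laboratory), in the same HLT by MedDRA coding", where the event is considered related.

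For AEs outside the protocol's grading system, Protocol 8.5.3.1 supplies a descriptive scale. Its severe category reads: "Events interrupt usual activities of daily living, or significantly affects clinical status, or may require intensive therapeutic intervention".

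**The concern.** A severity scale should not stop grading as results get worse. Here a transaminase of 5 x ULN is Grade 3 by the table, whatever the investigator thinks of its clinical significance, while 10 x ULN matches no band. The cap applies to AST and ALT alone. Bilirubin, the other liver marker, is open above 2.5 x ULN, and nothing in the documents explains the difference.

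The grade feeds a primary endpoint and a study halting rule in a first-in-human trial with 10 vaccinees per dose group, where one subject changes both the reported rate and the halting count. The protocol's own introduction lists hepatitis among the features of yellow fever. The vaccine is inactivated and liver injury is not expected, but transaminases are an obvious parameter to grade without gaps.

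**Working it through.** **1. Is the cap peculiar to AST and ALT?** Counting the laboratory Grade 3 cells in Appendix A:

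| Table | Grade 3 cells | Open-ended | Capped |
|---|---|---|---|
| 11 Hematology | 5 | 5 | 0 |
| 12 Blood chemistries | 12 | 12 | 0 |
| 13 Liver enzymes | 2 | 0 | 2 |
| 14 Urine dipstick | 4 | 4 | 0 |
| Total | 23 | 21 | 2 |

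**2. Grades from Table 13 as printed and with an open top band:**

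| Value (x ULN) | As printed | Grade 3 as ≥ 3.0 x ULN |
|---|---|---|
| 2.99 | Grade 2 | Grade 2 |
| 3.0 | Grade 3 | Grade 3 |
| 8.0 | Grade 3 | Grade 3 |
| 8.01 | none | Grade 3 |
| 10 | none | Grade 3 |
| 20 | none | Grade 3 |

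**3. Where an ungraded value goes.** It fits neither class of the 9.4.2 split. SAP Table 28 offers None and Grades 1 to 3, SAP Table 29 offers Grades 1 to 3, and neither has a rule that places the value. The 8.2.2 duties to assess relatedness and to follow up are written for graded results. An out-of-range result that does not meet the criteria leads to a repeat or referral only if it is judged clinically significant.

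**4. Effect on the estimate.** The interval method can be checked against the plan's own figure. For 0 events in 10, the two-sided exact upper limit is 1 − 0.025^(1/10) = 30.85%, against the stated 30.8% (Protocol 9.2.1, SAP section 5). The same Clopper-Pearson method gives:

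- 1/10 = 10%, 95% CI 0.25% to 44.50%
- 2/10 = 20%, 95% CI 2.52% to 55.61%

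**5. Illustration.** Two vaccinees in one dose group have related rises of the same enzyme, one to 5 x and one to 10 x ULN. As printed, one has a Grade 3 laboratory toxicity: the rate is 1/10 and the halting count is 1 against a threshold of 2. With an open top band the rate is 2/10 and the count is 2, which halts the trial for review by the Safety Monitoring Committee (SMC).

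The difference depends on two conditions:

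- The 10 x ULN subject has no other post-baseline value of that enzyme between 3.0 and 8.0 x ULN. The maximum rows in SAP Tables 28 and 29 include unscheduled tests, so one such value restores Grade 3.
- The event is not separately recorded as a Grade 3 AE, for the halting rule, or as a related SAE.

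**The case against.** The strongest reply is that such a value would not be ignored.

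- The AE definition in Protocol 8.5.1 includes abnormal laboratory findings, and 8.5.3.2 says doubtful cases should be reported. Once an AE is recorded, severity grading, relatedness assessment and follow-up are all required.
- Section 8.2.2 requires the investigator to document clinical significance for every out-of-range value, and to report a result that meets the SAE definition.
- The halting rule is a single count over unsolicited AEs and laboratory results. A 10 x ULN rise recorded as a related Grade 3 AE in the same MedDRA high-level term would join the 5 x ULN result. Any related SAE halts the trial by itself.
- The halting rule also needs a relatedness judgement at 5 x ULN. Automatic counting is strictly true only of the laboratory endpoint.
- SAP Table 28 does have a column headed Severe/Grade 3, so a programmer could place the value there.

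All of this stands, and it limits the consequence. It does not supply the missing grade. Whether the result is an AE, how severe it is and whether it is serious remain the investigator's judgements. It is also arguable whether the 8.5.3.1 scale applies, since AST and ALT are within the protocol's grading system. A Grade 3 AE record would enter a different primary outcome, not the laboratory one. Placing the value in the Severe column would be sensible, but no text instructs it.

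Other safeguards also remain. Before dose 2, "the most recently evaluated clinical safety laboratory values obtained prior to the second study vaccination must be Grade 1 or less". The SMC reviews laboratory data before escalation, and abnormal chemistry results are listed individually.

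**Conclusion.** The concern holds. Two of 23 laboratory Grade 3 cells are capped, and by the printed scale any AST or ALT above 8.0 x ULN has no laboratory grade. The laboratory endpoint counts the milder result by rule and leaves the worse one to judgement. In a group of 10, one affected subject shifts the observed Grade 3 laboratory rate by 10 percentage points and can decide whether the two-subject halting threshold is met, under the conditions given with the illustration.

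The documents give no rate for values above 8.0 x ULN. They should be uncommon in healthy adults screened at Grade 1 or less. The cap is probably a drafting slip, and a site would likely treat such a value as severe. The point is therefore a grading error that should be fixed because it touches a primary endpoint and a halting rule. It is not a finding that events would be lost.

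**What to change.** In Table 13, change the Grade 3 cells for AST and ALT to ≥ 3.0 x ULN, in line with the open top bands of the other laboratory tables.

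If the sponsor prefers to add a Grade 4 above 8.0 x ULN, the primary laboratory endpoint, the halting criteria and SAP Tables 9, 28 and 29 should then be defined as Grade 3 or higher. Otherwise the same gap reappears one grade up.

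The first option costs two table cells and the matching line of the grading program. No visits, samples or procedures change.

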1. PREFACE

The Statistical Analysis Plan for “A Double Blind, Randomized, Placebo-Controlled, Phase 1 Dose Escalation Trial to Evaluate the Safety and Immunogenicity of an Inactivated Yellow Fever Virus Vaccine, HydroVax-002 YFV, in Healthy Adults” (NTI protocol 20-001) describes the analyses to be performed for the interim and final analyses defined in the complete clinical protocol.

This document describes all planned analyses and provides reasons and justifications for these analyses. It also includes sample tables, listings, and figures planned for the analyses.

This document contains four major sections: (1) a review of the study design ([Section 2](#), [Section 3](#), [Section 4](#)), (2) sample size general statistical considerations ([Section 5](#), [Section 6](#)), (3) comprehensive statistical analysis methods for safety and immunogenicity outcomes ([Section 8](#), [Section 9](#)), and (4) a list of proposed tables and figures ([Section 13](#)). Any deviation from this analysis plan will be described and justified in the interim and final analysis reports, as appropriate. The reader of this analysis plan is encouraged to also review the study protocol for details on conduct of the study and the operational aspects of clinical assessments.

2. INTRODUCTION

This trial is a randomized, placebo controlled, double-blind (within dosing group), dose escalation Phase 1 trial evaluating dosages of 1 mcg and 5 mcg of HydroVax-002 YFV vaccine given intramuscularly on Day 1 (the day of first vaccination is defined as Day 1) and Day 29 in healthy adults ≥ 18 and < 50 years of age. The study consists of two dosing groups of HydroVax-002 YFV vaccine to be enrolled sequentially. Each dose group will consist of 10 individuals who receive HydroVax-002 YFV and 2 or 3 who receive placebo. The initial dose of HydroVax-002 YFV to be evaluated in Group 1 is 1 mcg and the next dose to be evaluated in Group 2 is 5 mcg. Following assessment of safety and reactogenicity data of Group 1 by the Safety Monitoring Committee (SMC), the vaccine dose was increased to 5 mcg for Group 2. An overview of the study design is provided in the complete clinical protocol.

2.1. Purpose of the Analyses

The protocol for NTI 20-001 calls for a planned interim analysis of safety, reactogenicity, and immune response data once all subjects have completed the Day 57 visit and the data are entered in the database, validated and monitored according to the clinical monitoring plan. This Statistical Analysis Plan encompasses both the planned interim analysis and final analysis. The goal of the interim analysis is to provide information for manuscript preparation. While the results will not be used to make any decisions concerning the conduct of this trial, they may be used to make decisions on activities external to this trial such as the design of future trials of this vaccine.

